**Table 2. Simulation results with 1000 patients (90% power)**

Simulation scenario	Hazard rate in warfarin (%/pt-yr)	Hazard rate in apixaban (%/pt-yr)	Rate of passing NI test*
Under the alternative hypothesis (Power)	1.75	1.75	89.4%
Under the null hypothesis (Type I error)	1.75	3.50	2.7%

\* The data were simulated 10,000 iterations.

## 6.2 Patient Characteristics

### 6.2.1 Patient Disposition

The patient disposition table will summarize the following and will be presented for all patients by treatment group and overall.

- The number (%) of patients withdrawn before the protocol-mandated end of study
- The number (%) of patients who completed the study at the end of study
- The number (%) of patients who followed for a minimum of 2 years
- The number (%) of patients who died during the study follow-up period
- The number (%) of patients who were lost to follow-up
- The number (%) of patients who experienced early discontinuation of their assigned treatment
- The number (%) of patients who were lost to follow-up
- Length of follow-up
- The number (%) of patients in the ITT population
- The number (%) of patients in the OT population
- The number (%) of patients in the AT population

### 6.2.2 Baseline Characteristics

Demographic data presented will be age, race and gender. Etiology, lesion, time from surgery and New York Heart Association (NYHA) functional class at screening will be presented as background data.

Demographic and background data will be summarized using summary statistics for continuous variables (number of patients, mean, standard deviation, median (Q1, Q3), minimum and maximum) or by way of group frequencies and percentages for categorical variables, as appropriate. These data will be presented for the ITT population.

### 6.2.3 Treatment Exposure and Compliance

For patients randomized to apixaban, patient compliance with the study intervention will be assessed by filling of the drug with a gap in filled supply >14 days defined as non-compliance.

For patients randomized to warfarin, patient compliance with the study intervention will be assessed by time in therapeutic range (TTR) using INR levels. TTR will be determined by Rosendaal's method that

assumes that the INR value between two measurements varies linearly from the first value to the second value. (Rosendaal et al. 1993)

- Let  $INR_i$  and  $INR_{i+1}$  be the two consecutive INR values
- Let  $D_i$  and  $D_{i+1}$  be the dates associated with these two consecutive INR values,  $[(D_{i+1} - D_i) = k, k > 1]$
- Assuming the linear increase or decrease between the two consecutive INR measurements, the unit change per day in INR is  $m = (INR_{i+1} - INR_i)/(D_{i+1} - D_i)$
- The estimated INR value for the date after  $D_i$  ( $D_{i+1}$ ) will be  $INR_i + (m \times 1)$
- Similarly, the estimated INR value for the date ( $D_{i+2}$ ) will be  $INR_i + (m \times 2)$ , etc.; the estimated INR value on the date immediately prior to  $D_{i+1}$  will be  $INR_i + (m \times (k - 1))$ .

Each patient randomized to warfarin will have an INR measurement every day, either actual or by estimation through linear interpolation. Percent time in INR target 2.0-3.0 (i.e. TTR) will be calculated in three ways:

- 1)  $100 \times (\text{total number of unique days where estimated or actual INR matches the specified INR regimen}) / (\text{total number of unique days from the date of the first INR value prior to/at randomization to the date of the last INR value prior to/at randomization})$
- 2)  $100 \times (\text{total number of unique days where } 2.0 \leq \text{estimated or actual INR value} \leq 3.0) / (\text{total number of unique days from the date of the first INR value after randomization to the date of the last INR value while on study drug warfarin})$
- 3)  $100 \times (\text{total number of unique days where } 2.0 \leq \text{estimated or actual INR value} \leq 3.0) / (\text{total number of unique days from the date of the first INR value after randomization to the date of the last INR value while in the study})$

The number (%) of compliant and noncompliant patients who took warfarin will be summarized using the ITT population.

#### 6.2.4 Concomitant Medications

All medications will be coded using the most recent version of the WHO Drug dictionary. The number (%) of patients reporting the use of any concomitant medications including non-study warfarin, except aspirin, and the number of reported concomitant medications will be summarized at randomization and after that by treatment group using the ITT population.

#### 6.2.5 Medical Histories

The number of patients reporting one or more conditions for past medical history will be summarized using counts and percentages. Both prior and concomitant medical conditions summaries will use the ITT population.

## 6.3 Efficacy Analysis

### 6.3.1 Primary Efficacy Variable

The co-primary analysis will be conducted for the primary efficacy outcome using the ITT population.

A linearized event rate per arm is defined as the total number of patients with adjudicated efficacy outcomes divided by the total patient time (years). The approximate 95% CI for the difference of linearized event rates will be calculated as

$$\left( \frac{r_A}{T_A} - \frac{r_W}{T_W} \right) \pm 1.96 \sqrt{\frac{r_A}{T_A^2} + \frac{r_W}{T_W^2}},$$

where subscript A and W denote the apixaban and warfarin arms, respectively, and r is the total number patients with adjudicated efficacy outcomes, and T is the total patient time (years). (Liu et al. 2006)

As the first co-primary analysis, if the upper bound of the 95% CI for the difference of linearized event rates is less than the non-inferiority margin of 0.0175/pt-yr (=1.75%/pt-yr), it will be concluded that apixaban is non-inferior to warfarin for the primary efficacy outcome in patients with an On-X mechanical heart valve implanted in the aortic position.

As the second co-primary analysis, if the apixaban arm achieves at least 800 pt-yrs and the linearized event rate is less than two times the OPC or 0.034/pt-yr (=3.4%/pt-yr), the OPC test is passed. (Wu et al., 2014)

Once both co-primary analyses are met using the ITT population, we declare success and that apixaban is a reasonable alternative to warfarin for thromboembolic event prevention in this population.

If a non-inferiority for the primary efficacy outcome is established, a superiority test for the primary efficacy outcome will be performed using the ITT population. If the upper bound of the 95% CI for the difference of linearized event rates is less than zero, it will be concluded that apixaban is superior to warfarin for the primary efficacy outcome in patients with an On-X mechanical heart valve implanted in the aortic position.

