### 6.3 Efficacy Analysis

#### 6.3.1 Primary Efficacy Variable

The co-primary analysis will be conducted for the primary efficacy outcome using the ITT population.

A linearized event rate per arm is defined as the total number of adjudicated efficacy outcomes divided by the total patient time (years). The approximate 95% CI for the difference of linearized event rates will be calculated as

$$\left( \frac{r_A}{T_A} - \frac{r_W}{T_W} \right) \pm 1.96 \sqrt{\frac{r_A}{T_A^2} + \frac{r_W}{T_W^2}},$$

where subscript *A* and *W* denote the apixaban and warfarin arms, respectively, and *r* is the total number of adjudicated efficacy outcomes, and *T* is the total patient time (years). (Liu et al. 2006)

As the first co-primary analysis, if the upper bound of the 95% CI for the difference of linearized event rates is less than the non-inferiority margin of 0.0175/pt-yr (=1.75%/pt-yr), it will be concluded that apixaban is non-inferior to warfarin for the primary efficacy outcome in participants with an On-X mechanical heart valve implanted in the aortic position.

As the second co-primary analysis, if the apixaban arm achieves at least 800 pt-yrs and the linearized event rate is less than two times the OPC or 0.034/pt-yr (=3.4%/pt-yr), the OPC test is passed. (Wu et al., 2014)

Once both co-primary analyses are met using the ITT population, we declare success and that apixaban is a reasonable alternative to warfarin for thromboembolic event prevention in this population.

If a non-inferiority for the primary efficacy outcome is established, a superiority test for the primary efficacy outcome will be performed using the ITT population. If the upper bound of the 95% CI for the difference of linearized event rates is less than zero, it will be concluded that apixaban is superior to warfarin for the primary efficacy outcome in participants with an On-X mechanical heart valve implanted in the aortic position.

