### 1.2 Study Design

This is a prospective, multicenter, open-label, randomized, active controlled clinical trial to determine if patients with an On-X aortic valve, alone or as an On-X Ascending Aortic Prosthesis, can be maintained safely and effectively on apixaban. The primary outcome is a composite rate of valve thrombosis and valve-related thromboembolism, which will be used for co-primary analyses. The first co-primary analysis will determine whether apixaban is non-inferior to warfarin (INR target range 2.0 - 3.0) in patients with an On-X mechanical heart valve implanted in the aortic position. The second co-primary analysis will compare the composite rate for apixaban-treated patients to updated OPC for FDA-approved mechanical heart valves in the aortic position. Each patient will be followed for at least 2 years and each randomized arm will achieve at least 800 pt-yrs.

The study will consist of approximately 1000 patients (randomized 1:1 with approximately 500 patients in the apixaban arm and 500 patients in the warfarin arm) at a minimum of 3 sites and up to 60 sites in North America, and potentially in Europe and/or Japan, who are 18 years of age or older, at least 3 months out from an On-X aortic valve implantation, and currently managing their anticoagulation with warfarin.

Patients will be randomized to either continue warfarin or switch to apixaban. Patients randomized to apixaban will receive 5 mg twice daily (BID), or apixaban 2.5 mg BID in patients with 2 or 3 of the following characteristics:

- age  $\geq$  80 years
- weight  $\leq$  60 kilograms
- creatinine  $\geq$  1.5 mg/dL (133 micromol/L)

For patients randomized to apixaban, INR testing will be performed on the current warfarin dose with the following algorithm to initiate apixaban:

1. INR  $<$  2; stop warfarin and start apixaban

2. INR 2.0 to 3.0; hold warfarin for 2 days, start apixaban on day 3
3. INR > 3.0 to 4.0; hold warfarin for 4 days, start apixaban on day 5
4. INR > 4.0; hold warfarin for 2 days, recheck INR, refer to steps 1, 2, or 3

The procedures to be performed throughout the study are outlined in the Schedule of Activities in the study protocol (see Section 1.1 of the study protocol).

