## 6 Statistical Methodology

### 6.1 Statistical and Analytical Issues

#### 6.1.1 General principles

Statistical methods will be based on the International Conference on Harmonization (ICH) E9 document “Statistical Principles for Clinical Trials”. All hypothesis testing will be carried out at the 2.5% (1-sided) significance level unless otherwise specified. P-values will be rounded to three decimal places. P-values less than 0.001 will be reported as <0.001 in tables. P-values greater than 0.999 will be reported as >0.999. All statistical analysis will be performed using SAS® v9.4 or higher (Cary, NC USA).

In summary tables of continuous variables, the minimum and maximum statistics will be presented to the same number of decimal places as the original data. The arithmetic mean (AM), median (Q1, Q3), 95% confidence interval (CI), standard deviation (SD) and standard error (SE) will be presented to one more decimal place than the original data. In the event no meaningful information is available through the aforementioned decimal place, the statistician in consultation with the PI or designee will determine the most relevant number of decimals to display. Summaries of continuous characteristics will be based on non-missing observations.

In summary tables of categorical variables, counts and percentages will be used. The denominator for each percentage will be the number of patients with non-missing values for the variable within the population treatment group unless otherwise specified. In the event that the summary displayed is for a subcategory (“child”) of a main category (“parent”), the denominator for the “child” will be based on the non-missing observations for the “parent” (e.g., Heart Failure (Y/N) is a “parent” question and Heart Failure Functional Class (e.g. Class I) is a “child” question. The denominator for Class I will be number of patients who answered yes/no to the Heart Failure question).

Unless otherwise specified in this document, relative study day is defined as the (assessment date of a measurement – randomization date) if assessment date is prior to randomization date and will be defined as (assessment date of measurement – randomization date) + 1 if assessment date is on/after date of randomization. Using this derivation, the day of randomization will be considered study day 1.

Data displayed by visit will utilize an “analysis visit” which will be derived based on windowing outlined in section 6.1.2.

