### 6.1.8 Determination of Sample Size

With an expected accrual time of 1 year, an assumption that 50% of the expected number of patients will be enrolled in about 5 months (40% of the total accrual time), and a minimum follow-up period of 2 years, the assumed loss to follow-up rate for the period of 2 years is 5%, which is equivalent to a loss hazard rate of 0.026 for both the test and control groups. Assuming one-sided alpha of 2.5%, an

approximate power of 90%, an equal event rate of 1.75%/pt-yr in both warfarin and apixaban arms, and an absolute NI margin of 1.75%/pt-yr, the estimated sample size is 990, therefore this study will recruit approximately 1000 patients. Refer to Section 8.2 of the study protocol for the full sample size calculation and the NI margin justification.

As noted in Table 1 showing the expected statistical power based on observed event rates with 1000 patients, the power to rule out an absolute difference of 1.75%/pt-yr or a hazard ratio of 2 is greater than 70% for all scenarios where the event rates for the warfarin and apixaban arms are less than 2.8%/pt-yr. Based on historical trials with warfarin anticoagulation and the On-X valve, the hazard rate in warfarin arm is expected to be  $\leq 2.8\%$ /pt-yr. However, recognizing the uncertainty regarding the background event rate in warfarin arm, the study is designed to have the co-primary analysis with the NI and OPC tests as described in Section 1.1.1 of this document. Also, as a sensitivity analysis, a proportional hazard regression model with a hazard ratio of 2 for the NI margin will be performed.

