## 6.4 Safety Analysis

### 6.4.1 Primary Safety Variable

Major bleeding as a primary safety outcome will be tested for a superiority by a log-rank test with a one-sided significance level of 0.025 using the AT population. Time from the study drug initiation date to the date of first adjudicated major bleeding or censoring will be determined as specified in Section 6.1.6.

A linearized event rate per arm is calculated as the total number of patients with adjudicated major bleeding divided by the total patient time (years) using the AT population. The major bleeding rate for both warfarin and apixaban arms will be compared with two times the major hemorrhage OPC, or 0.032/pt-yr (=3.2%/pt-yr). (Wu et al., 2014)

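### SAP v1.4 counts each patient once in the primary rate but never ends patient time at the first event; on the plain reading both rates read low and their difference shrinks toward zero

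*Combined protocol and SAP*

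**What the plan says.** **Primary rate.** SAP v1.4, 6.3.1, sets the rate in each arm as "the total number of patients with adjudicated efficacy outcomes divided by the total patient time (years". The same r and T enter the Wald interval for the difference. In the earlier SAP, 6.3.1, the numerator was different: "the total number of adjudicated efficacy outcomes divided by the total patient time (years". The denominator wording is the same in both. The revision history in SAP v1.4 does not explicitly list a change of numerator.

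**Decision rules.** Non-inferiority requires the upper 95% bound of the difference to be "less than the non-inferiority margin of 0.0175/pt-yr (=1.75%/pt-yr" per year. The OPC test requires at least 800 patient-years on apixaban and a point estimate below 3.4%/pt-yr. Both rules use the rate above.

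**Bleeding.** SAP v1.4, 6.4.1, builds its descriptive rate in the same way: "the total number of patients with adjudicated major bleeding divided by the total patient time (years) using the AT population".

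**Time rules elsewhere.** SAP v1.4, 6.1.5, gives a general ITT time that ends at the event date when an event occurs, and 6.1.6 gives the censoring dates. Section 6.3.1 cites neither. Section 6.4.1 cites 6.1.6 for the log-rank time, and 6.8 does so for the Cox and bleeding sensitivity analyses.

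**Follow-up after an event.** Protocol 5.9 keeps participants in the study after a thrombotic or bleeding event even if they change or stop anticoagulation.

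**The concern.** The hypotheses in Protocol 8.1 and SAP v1.4, 6.1.8, concern hazard rates under an approximately exponential model. Two ratios estimate such a rate consistently: first events over time to first event, and, if the rate stays constant after an event, all events over all time. A mixture of the two does not. A patient counted once can add nothing to r after a first event, but under the plain reading goes on adding to T.

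The dilution is greater in the arm with more events, so the difference moves toward zero. At the margin, where apixaban is worse, this makes a false finding of non-inferiority more likely. It also lowers the apixaban rate that is compared with 3.4%, and that rule has no confidence bound to absorb a bias. Both co-primary tests therefore depend on a denominator that the primary-analysis section does not pin down, in an open-label trial.

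**Working it through.** **Inputs**
- Test level (SAP v1.4, 6.1.1): "All hypothesis testing will be carried out at the 2.5% (1-sided) significance level unless otherwise specified".
- Planning values (6.1.8): "approximate power of 90%, an equal event rate of 1.75%/pt-yr in both warfarin and apixaban arms, and an absolute NI margin of 1.75%/pt-yr".
- Allocation (1.2): "randomized 1:1 with approximately 500 patients in the apixaban arm and 500 patients in the warfarin arm".
- Accrual over 1 year with half enrolled by 0.4 years, minimum follow-up 2 years, 5% loss over 2 years (6.1.8). Loss hazard = −ln(0.95)/2 = 0.0256.
- Null scenario (Table 2, warfarin then apixaban): "Under the null hypothesis (Type I error) 1.75 3.50 2.7"%. The text of 6.1.8 states these two rates with the arms swapped. Table 2 has the order that fits the null hypothesis and is used here.
- Entry is taken as truncated exponential, with events exponential.

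**Step 1: reproduce the plan.** n per arm = (1.960 + 1.282)² × [λA²/P(event, A) + λW²/P(event, W)] / (margin − true difference)². At 1.75% in both arms, P(event) = 0.0425 and λ²/P = 0.00720. So n = 10.51 × 0.01441 / 0.0175² = 494.4, rounded up to 495 per arm or 990 in total, as stated. Power at 500 per arm is 90.3%, as stated in Table 1.

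**Step 2: expected rates at the margin, planned follow-up.** Mean follow-up is 2.484 years, so total time is 500 × 2.484 = 1,242 pt-yr per arm.

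| | Warfarin, true 1.75 | Apixaban, true 3.50 | Difference |
|---|---|---|---|
| Expected patients with an event | 21.25 | 41.57 | |
| Time to first event (pt-yr) | 1,214.5 | 1,187.9 | |
| Rate, T stops at first event | 1.75 | 3.50 | 1.75 |
| Rate, T is all follow-up (1,242) | 1.71 | 3.35 | 1.64 |

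The warfarin rate is 2.2% too low in relative terms and the apixaban rate 4.4% too low.

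**Step 3: false non-inferiority, normal approximation.** The pass probability is Φ[(0.0175 − expected difference)/SE − 1.96], with SE = √(rA/TA² + rW/TW²).
- All follow-up: SE = √(41.57 + 21.25)/1,242 = 0.00638. Φ[(0.0175 − 0.01636)/0.00638 − 1.96] = Φ(−1.78) = 3.7%.
- Time to first event: SE = 0.00662. Φ(−1.96) = 2.5%.

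**Step 4: simulation of the SAP rule, 500 per arm.** False non-inferiority is about 3.7 to 3.8% with all follow-up, against 2.9 to 3.0% with time to first event. All events over all time gives 2.9%. The Wald interval itself accounts for the part above 2.5% in the last two, so the mixture adds about 0.8 points. Over warfarin rates of 1.09 to 2.81% (the confidence limits in Protocol 8.2), with apixaban 1.75 points higher, it is 3.9 to 3.3% against 3.1 to 2.5%.

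**Step 5: other true differences.** At equal rates of 1.75% the difference is unbiased, and simulated power is about 91.7 to 91.8% against 90.0%. With warfarin at 3.50 and apixaban at 1.75, the expected difference is −1.63 instead of −1.75.

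**Step 6: OPC rule at a true 3.4%.** Expected patients with an event are 40.4, and 40.4/1,242 = 3.26%. SE = √40.4/1,242 = 0.51%. Φ[(3.40 − 3.26)/0.51] is about 61%. By simulation it is 62 to 63%, against 50 to 51% when T stops at the first event.

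**Step 7: shorter follow-up (assumed).** SAP v1.4, 6.1.3, reports the early stop but gives no patient-years. At about 820 pt-yr per arm, false non-inferiority is 3.3% against 2.95%. At about 510 pt-yr it is 3.3% against 3.15%. At about 820 to 830 pt-yr a true 3.4% passes the OPC rule 56 to 58% of the time, against 51 to 52%. Below 800 pt-yr the OPC test cannot be passed under either definition of T.

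**The case against.** The strongest reply is that the SAP never says post-event time is kept. Section 6.1.5 supplies a general ITT time that ends at the event, and if T follows it there is nothing to correct. The plan's own simulation points the same way. Table 2 reports 2.7% type I error and 89.4% power from 10,000 runs, with standard errors of √(0.027 × 0.973/10,000) = 0.16 points and √(0.894 × 0.106/10,000) = 0.31 points. Those figures fit time to first event (2.9% and 90.0%) and not the mixture (3.7% and 91.8%). This stands as evidence of intent. It does not define T: 6.1.5 concerns time to event, a term 6.3.1 does not use, and in 6.4.1 the first-event time is given for the log-rank test but not for the rate that follows.

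A reader might infer that the SAP states a biased estimator outright, or that the difference is always biased in apixaban's favour. The documents support neither. The first depends on how T is read. The second fails at Step 5: there is no bias at equal rates, which is the planning alternative, and the bias runs against apixaban when it is better.

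The effect is also small. Fatal first events add no post-event time and would reduce it further. The OPC contrast is taken exactly on the limit, where a point rule passes about half the time by construction. The Cox sensitivity analysis in 6.8 uses first-event time, but against a hazard ratio of 2, so it does not replace the primary test. Finally, the documents do not show which SAP revision changed the numerator. Version 1.2 lists a change to the time-to-event calculation, and the numerator may have changed with it.

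**Conclusion.** The point holds as an undefined denominator whose plain reading does not estimate the hazard rate under test. The mismatch between numerator and denominator is in the text; the bias is conditional on T including time after the first event. On that reading the excess false non-inferiority is about 0.8 points at planned follow-up, falling to about 0.3 points near 800 pt-yr per arm and about 0.15 points near 510. The last two rest on assumed patient-years, and all of them on exponential events and full follow-up after non-fatal events. The effect on the OPC rule at its limit is about 12 points at planned follow-up and about 5 to 6 points near 820 to 830 pt-yr. For bleeding, only the rate set against 3.2%/pt-yr is affected; the log-rank test is not. This is a modest but avoidable weakness that should be closed, not a defect that by itself undermines the trial.

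**What to change.** In SAP v1.4, 6.3.1 and 6.4.1, define T in the rate as the sum over patients of time from the population's start date (randomization for ITT, study drug initiation for AT) to the first adjudicated event of that outcome or censoring, citing 6.1.5 and 6.1.6. State separately that the 800 patient-year requirement still refers to cumulative follow-up, as in Protocol 4.4. Report all adjudicated events over all follow-up time as a supporting rate, and record the change of numerator in the revision history.

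The cost is a sentence or two in each section. The first-event times are already derived for the Cox and log-rank analyses, so no new data are needed. The only statistical price is that apparent power at equal rates of 1.75% falls from about 91.7% to the planned 90%.

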**Table 1. Expected statistical power by event rate and statistical method with 1000 patients**

Event rate in warfarin arm (%/pt-yr)	Event rate in apixaban arm (%/pt-yr)	Hazard rate approach with a NI margin of 1.75%/pt-yr	Hazard ratio approach with a NI margin of 2.0
1.00	1.00	99.1%	33.8%
1.25	1.25	97.2%	40.6%
1.50	1.50	94.1%	47.0%
1.75	1.75	90.3%	52.9%
2.00	2.00	86.1%	58.3%
2.25	2.25	81.8%	63.3%
2.50	2.50	77.5%	67.8%
2.80	2.80	72.6%	72.5%
3.00	3.00	69.5%	75.3%
3.50	3.50	62.5%	86.0%
4.00	4.00	56.6%	100.0%
4.50	4.50	51.5%	100.0%
5.00	5.00	47.2%	100.0%

The empirical type I error rate and power were evaluated using Markov chain Monte Carlo simulations with 10,000 iterations per scenario as presented in Table 2. The hypothesis statements are as follows:

$$H_0: \lambda_{\text{apixaban}} - \lambda_{\text{warfarin}} \geq 1.75\%/\text{pt-yr}$$

$$H_A: \lambda_{\text{apixaban}} - \lambda_{\text{warfarin}} < 1.75\%/\text{pt-yr},$$

where  $\lambda$  is the hazard rate of the primary efficacy outcome. The type I error rate was calculated as a proportion of rejecting the null hypothesis, i.e., how many times the upper bound of the 95% CI of hazard rate difference is less than the NI margin of 1.75%/pt-yr, when simulated 10,000 iterations under the null hypothesis ( $\lambda_{\text{apixaban}}=1.75\%/\text{pt-yr}$  and  $\lambda_{\text{warfarin}}=3.50\%/\text{pt-yr}$ ). The empirical power was calculated in the same way when simulated 10,000 iterations under the alternative hypothesis ( $\lambda_{\text{apixaban}}=1.75\%/\text{pt-yr}$  and  $\lambda_{\text{warfarin}}=1.75\%/\text{pt-yr}$ ).

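### The Wald limit that decides non-inferiority has a true one-sided error of about 2.9% at the planned exposure, against the stated 2.5%; the excess is small, partly disclosed and not corrected

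*Combined protocol and SAP*

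**What the plan says.** SAP v1.4, section 6.3.1, takes the rate in each arm as patients with an event divided by patient-years. It forms the 95% interval for the difference as (r_A/T_A − r_W/T_W) ± 1.96·√(r_A/T_A² + r_W/T_W²), which it calls approximate. Non-inferiority is concluded "if the upper bound of the 95% CI for the difference of linearized event rates is less than the non-inferiority margin of 0.0175/pt-yr". Success also requires the OPC test: at least 800 pt-yr on apixaban and an apixaban rate below 3.4%/pt-yr.

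Section 6.1.1 states: "All hypothesis testing will be carried out at the 2.5% (1-sided) significance level unless otherwise specified".

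Section 6.1.8 aims for about 90% power, taking 1.75%/pt-yr as the true rate in each arm. It states that with "an absolute NI margin of 1.75%/pt-yr, the estimated sample size is 990". Its Table 2 reports a simulated pass rate of 2.7% in the row that begins "Under the null hypothesis (Type I error", for warfarin 1.75 and apixaban 3.50. The text before that table, describing the pass rate "when simulated 10,000 iterations under the null hypothesis", gives the rates the other way round (apixaban 1.75, warfarin 3.50). The same reversal stands in section 6.1.4 of the earlier SAP in the file.

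**The concern.** The standard error comes from the observed counts, not from rates that differ by the margin. When the apixaban count is low by chance, the estimated difference and its standard error shrink together. The upper limit then falls below 1.75%/pt-yr more often than 2.5% of the time when the true difference equals the margin. This happens at the planned counts, about 42 against 21 patients with events, and is not a zero-cell problem. It affects the error rate of the claim that, per the SAP introduction, would support a change to the device label.

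The excess grows as the warfarin rate falls, and a lower rate is plausible. The 1.75%/pt-yr planning rate in protocol section 8.2 includes valve-related mortality, which is not part of the primary outcome.

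**Working it through.** **1. Reproduce the plan's sample size.** Inputs from SAP 6.1.8: 1 year of accrual with half enrolled by 0.4 year, 2 years' minimum follow-up, loss hazard η = 0.026, λ = 0.0175 in both arms, margin δ = 0.0175. Entry times are truncated exponential on 0-1 year, with the rate set so that half have entered by 0.4 year.

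P(event) = λ/(λ+η) · E[1 − exp(−(λ+η)(3−t))] = 0.0425

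n per arm = 2·(λ²/P)·(1.960+1.282)²/δ². Since λ = δ, this is 2 × 10.51/0.0425 = 494.6, so 495 per arm and N = 990, as stated. With 500 per arm the power is Φ(√(0.0425 × 500/2) − 1.960) = Φ(1.30) = 90.3%, as in Table 1.

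**2. Exposure.** The same assumptions give about 1,214 pt-yr per arm at 1.75%/pt-yr (21 events) and 1,187 at 3.50%/pt-yr (42 events).

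**3. Error of the rule.** For independent Poisson counts with apixaban rate = warfarin rate + 1.75, add the probabilities of all count pairs whose Wald upper limit is below 0.0175. The score rule uses the same δ but takes the variance from rates constrained to differ by δ:

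z = (r_A/T_A − r_W/T_W − δ)/√((λ₀+δ)/T_A + λ₀/T_W)

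where λ₀ is the positive root of Sλ² + (Sδ − r_A − r_W)λ − r_W·δ = 0 and S = T_A + T_W. It passes if z < −1.96.

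Pass rates (%) on the null boundary, at 1,187 pt-yr in each arm unless marked:

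| Warfarin / apixaban (%/pt-yr) | Wald | Score | Wald and OPC | Wald, 800 pt-yr per arm |
|---|---|---|---|---|
| 1.09 / 2.84 | 3.16 | 2.35 | 3.16 | 3.46 |
| 1.19 / 2.94 | 3.12 | 2.35 | 3.12 | 3.37 |
| 1.75 / 3.50 | 2.89 | 2.37 | 2.88 | 2.97 |
| 2.50 / 4.25 | 2.72 | 2.42 | 2.06 | 2.79 |
| 2.81 / 4.56 | 2.69 | 2.42 | 1.25 | 2.75 |

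At 800 pt-yr the score rule gives 2.2-2.35%. Patient-level simulation with the plan's accrual and loss gives Wald error of 2.88% at 1.75 (Monte Carlo error 0.02) and 3.15% at 1.09 (0.04). Counts are discrete, so the figures move by about 0.1 point with exposure: over 1,100-1,250 pt-yr the 1.75 row runs from 2.83 to 2.97. The 800 pt-yr entries at low rates sit at the upper end of their local range; averaged over 770-830 pt-yr they are 3.2-3.3.

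**4. Where the lower rates come from.** 1.09 and 2.81 are the confidence limits of the pooled warfarin rate in protocol 8.2. 1.19 is a crude pool made for this point from protocol Table 3, counting thromboembolism and thrombosis only: (8+6+7+19+1+16+2) + 2 = 61 events in 1360 + 659 + 411.8 + 1090 + 343.5 + 1069.4 + 172.5 = 5,106 pt-yr. The documents do not print it.

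**5. The SAP's 2.7%.** Its Monte Carlo error is √(0.027 × 0.973/10,000) = 0.16 points, so the 95% range is about 2.4-3.0%. It agrees with 2.9%.

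**6. A case where the choice matters.** 28 apixaban v 21 warfarin events, 1,206 pt-yr per arm. Difference 7/1,206 = 0.580%. Wald upper limit 0.580 + 1.96 × √49/12.06 = 1.718%: pass. Score: λ₀ = 1.383%, standard error √((0.03133 + 0.01383)/1,206) = 0.612%, z = (0.580 − 1.75)/0.612 = −1.91, one-sided p = 0.028: fail.

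**7. Power at 1.75 v 1.75.** Wald 89.9% and score 87.5% at 1,206 pt-yr per arm (90.0% and 87.7% at 1,214).

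**8. The reversed sentence.** With apixaban 1.75 and warfarin 3.50 the true difference is −1.75, and the rule passes 99.97% of the time. The printed 2.7% can only belong to Table 2's assignment.

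**The case against.** The plan is open about the approximation: it uses that word, it simulated this rule, and it prints 2.7% against a nominal 2.5%. The practical effect is slight. The true difference at which the Wald rule errs exactly 2.5% of the time is about 1.80%/pt-yr, a shift of about 0.05, which is minor beside a margin taken from a pooled rate with limits of 1.09 and 2.81. Success also needs the OPC test, which brings joint false success to 2.1% at warfarin 2.5 and 1.3% at 2.81. The score rule is not exactly 2.5% either; it errs on the conservative side and costs power. SAP v1.4, section 6.1.3, records that the study had already been stopped for safety, so changing a pre-specified decision rule there is not a mere wording edit.

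Most of this stands, and it limits the point without removing it. The OPC test does not help at warfarin rates of 1.75 or below, and the SAP checked only one null point.

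Two stronger readings are not supported. A reader might infer an error of 3.5% in the trial as planned; with planned follow-up that needs a warfarin rate of about 0.75 or less, below the plan's lower limit of 1.09. A reader might also infer from the reversed sentence that the simulation was run under the wrong scenario; step 8 shows that it was not.

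**Conclusion.** The rule in 6.3.1 does not deliver the stated 2.5%. With planned follow-up its error is about 2.9% at the planning rate and 3.1-3.2% at warfarin rates of 1.09-1.19, an excess of 0.4-0.7 points. At exactly 800 pt-yr per arm the figures are 3.0% and 3.4-3.5%. Below 800 apixaban pt-yr the OPC test cannot pass, so success cannot be declared and the question does not arise. The SAP disclosed the excess at one point, slightly low through simulation noise, and left it uncorrected.

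The result assumes constant hazards, the accrual and loss pattern of 6.1.8, and one event per patient. The actual counts after the early stop may differ. The point is worth correcting because the remedy is cheap, but it does not by itself discredit a clear result; it matters for a borderline one such as 28 v 21. The reversed null scenario is a separate text slip and adds nothing to the argument about the interval.

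**What to change.** - In 6.3.1, base the non-inferiority decision on a score limit for the difference of two person-time rates, with variance from rates constrained to differ by the margin (Miettinen-Nurminen type). Keep the Wald interval as descriptive.
- In 6.1.8, restate power at 1.75 v 1.75 as about 87.5% and re-run Table 2 with the score rule over warfarin rates of 1.09-2.81.
- Because v1.4 post-dates the safety stop, if the pre-specified Wald rule is kept, report the score limit beside it and state the Wald rule's error as about 2.9%.
- Separately, swap the two rates in the sentence defining the null scenario (v1.4 section 6.1.8 and section 6.1.4 of the earlier SAP) so that it agrees with Table 2.

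Cost: SAP text, a few lines of code and about 2.4 points of stated power. No patients are added if 87.5% is accepted; restoring 90% under the score rule would have needed about 545-550 per arm.
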